2.3.3 Exploratory Variable

The exploratory endpoint is recurrence of the target ulcer within follow-up period evaluated in those subjects who demonstrated complete wound healing at the end of comparison period.

3 STUDY POPULATION

3.1 Selection of Study Population

A total of 236 subjects will be randomized to ensure that approximately 212 subjects are evaluable. Evaluable subjects for this study mean all randomized subjects taking at least one dose of study treatment. The study will be conducted as multi-center trial. All sites will maintain a log of subjects screened for study entry and will document the reasons for exclusion for each subject not entered. The log of all subjects screened will be maintained in the Investigator Site File at the investigational site.

Additional sites may be initiated and non-productive sites may be closed to ensure sponsor timelines. Subjects who were already randomized in the study are not allowed to reenter.

3.2 Inclusion Criteria

Subject is eligible for the study if all of the following apply:

1. Has signed a written informed consent prior to the first study evaluation
2. Male or female is at least 20 and < 80 years of age
3. Diabetes mellitus (type 1 or 2) with an HbA1c < 12.0% measured during screening or within three months prior to randomization
4. An ankle brachial index on the target limb at least 0.8 measured during screening or within three months prior to randomization
5. The target ulcer must have the following characteristics:
 - a、 Grade 1 or 2 per Wagner Ulcer Classification System
 - b、 No higher than the ankle
 - c、 No active infection
 - d、 A cross-sectional area of between 1 and 25 cm² post-debridement
 - e、 Present for at least 4 weeks before randomization
6. If female and of childbearing potential has a negative pregnancy test and is not breastfeeding at screening visit
7. Able and willing to attend the scheduled visits and comply with study procedures

3.3 Exclusion Criteria

Subject will be excluded from participation if any of the following apply:

1. Presence of necrosis, purulence or sinus tracts that cannot be removed by debridement
2. Acute Charcot's neuroarthropathy as determined by clinical and/or radiographic examination

3. Has undergone revascularization procedure aimed at increasing blood flow in the treatment target limb < 4 weeks prior to randomization
4. Poor nutritional status defined as an albumin < 2.5 g/dL
5. AST and/or ALT >3 × the normal upper limit
6. Serum Creatinine >2 × the normal upper limit
7. Treatment with immunosuppressive or chemotherapeutic agents, radiotherapy or systemic corticosteroids within the 4 weeks before randomization
8. Use of any investigational drug or therapy within the 4 weeks prior to randomization
9. A psychiatric condition (e.g., suicidal ideation), current or chronic alcohol or drug abuse problem, determined from the subject's medical history, which, in the opinion of the Investigator, may pose a threat to subject compliance
10. Judged by the investigator to be not suitable for the study for any other reason

3.4 Discontinuation Criteria for Individual Subjects

A discontinuation is a subject who is randomized into the study and for whom study treatment is terminated prematurely for any reason.

The subject is free to withdraw from the study intervention and/or study for any reason and at any time without giving reason for doing so and without penalty or prejudice. The investigator is also free to terminate a subject's involvement in the study at any time if the subject's clinical condition warrants it.

Discontinuation Criteria for Individual Subjects:

1. Violation and/or significant deviation of study protocol
2. Lack of efficacy satisfactory (defined as a worsening of Wagner grade to level of 3)
3. Safety concerns
4. Lost to follow-up
5. Withdrawal consent;
6. In the Investigator's opinion, it is in the patient's best interest;
7. Termination of study by the sponsor.

In all cases, the reason for and date of withdrawal must be recorded in the case report form (CRF) and in the subject's medical records. The subject must be followed up to establish whether the

reason was an adverse event, and, if so, this must be reported in accordance with the adverse events reporting procedures.

If a subject withdraws from the study or the study intervention is discontinued prematurely, all procedures as scheduled at the end of the trial should be included on the case report form.

There will be no replacement of withdrawn subjects, regardless of the reason for withdrawal. All subjects who experience adverse event which is ongoing either at the time of withdrawal or at the post study visit, must be followed-up at appropriate time intervals until the adverse event is resolved or judged to be no longer clinically significant, or until they become chronic to the extent that they can be fully characterized.

4 STUDY TREATMENTS

4.1 Description of Study Interventions

4.1.1 Test Intervention

The study intervention is ON101, containing 1.25% of extracts of *Plectranthus amboinicus* and *Centella Asiatica*, available as cream for topical administration.

The following described the composition of ON101 cream.

Code Name ON101 cream

Component Dry extracts of PA-F4 and S1 (1:4 ratio)

<Cream Base: Cetostearyl alcohol, ~~Hexane~~, Liquid petrolatum, Methyl paraben Propyl paraben, Span 60, Tween 60, White petrolatum, water and pigments>

Amount per tube 1.25% ON101-DS in cream base, 15g cream per tube

4.1.2 Comparative Intervention

As a comparator, Aquacel[®] Hydrofiber[®] dressing (ConvaTec) is used. Aquacel[®] Hydrofiber[®] dressing maintains a moist wound environment for optimal healing, debridement and easy removal. Innovative dressing composed of sodium carboxy-methylcellulose fibers for the management of exudating wounds. This dressing is soft, nonwoven, conformable and highly absorbent.

4.2 Packaging and Labeling

All interventions used in this study will be packed, and labeled under the responsibility of a qualified person at Oneness Biotech Co., Ltd. and/or the designee in accordance with Standard Operating Procedures (SOPs), Good Manufacturing Practice (GMP) guidelines, International Conference on Harmonization guidelines for Good Clinical Practice (ICH GCP) guidelines, and applicable local laws/regulations.

4.3 Study Intervention Handling

Current ICH GCP Guidelines require the investigator to ensure that study medication deliveries from the sponsor are received by a responsible person (e.g. pharmacist), and

- that such deliveries are recorded;
- that study intervention is handled and stored safely and properly;
- that study intervention is only dispensed to study subjects in accordance with the protocol;
- that any unused study intervention is returned to the sponsor or standard procedures for the alternative disposition of unused study drug are followed.

Treatment inventory and accountability records for the study medication will be kept by the investigator/pharmacist. Study medication accountability throughout the study must be documented. The following guidelines are therefore pertinent:

- The investigator agrees not to supply study interventions to any persons except the subjects in this study.
- The investigator/pharmacist will keep the study interventions in a pharmacy or other locked and secure storage facility under controlled storage conditions, accessible only to those authorized by the investigator to dispense these test treatment.
- A study treatment inventory will be maintained by the investigator/pharmacist. The inventory will include details of material received and a clear record of when they were dispensed and to which subject.
- At the conclusion or termination of this study, the investigator/pharmacist agrees to conduct a final intervention supply inventory and to record the results of this inventory on the Treatment Accountability Record. It must be possible to reconcile delivery records with those of used and returned medication. Any discrepancies must be accounted for. Appropriate forms of deliveries and returns must be signed by the person responsible.
- Used or unused study intervention may be destroyed at the study center according to standard institutional procedures after drug accountability has been conducted by the Sponsor or representative, only if agreed upon by the Sponsor. A copy of the standard institutional procedure for destroying investigational treatment will be provided to the Sponsor or designee upon request. Unused study interventions not destroyed at the site must be returned to the Sponsor or designee at the end of the study or upon expiration.

4.4 Blinding

The investigator and research staff will not know the randomization assignment at the time of subject be screened to ensure they do not accidentally notify the subject of their assignment. After obtained a signed written informed consent and all study entry criteria has been confirmed, the investigator will be informed of the randomized treatment assignment by opening the individual treatment code envelope.

However, this study is developed as evaluator blind. A blinded independent evaluator, blinded to subjects' treatment, will evaluate the digital photograph on whether the wound has healed, defined as epithelialization wound. The results by a blinded independent evaluator will be used for primary analysis in this study.

4.5 Assignment and Allocation

Subjects who meet the inclusion and exclusion criteria will be randomly assigned to receive ON101 cream or Aquacel[®] Hydrofiber[®] dressing using a 1:1 randomization schedule. The schedule will be designed to balance the treatment arms by assigning eligible subjects from each study site in block randomization scheme. Individual investigators are blinded to the size of the block, eliminating the possibility that a prospective subject's assignment could be determined before randomization. Subject numbers assigned to subjects that do not receive study intervention will not be reused.

5 TREATMENTS AND EVALUATION

The following sections describe the procedures to be completed at screening and during the study. Subjects are to be assessed by the same investigator or site personnel whenever possible.

The following table details the study schedule of procedures for study period:

Schedule of Assessments

Assessments	Screening	Baseline	Comparative Period (up to 16 weeks)								Follow-Up [@]			
			3	4	5	6	7	8	9	10 ^{&}	11	12	13	14
Visit Number	1	2 [#]												
Visit Weeks	-1		2	4	6	8	10	12	14	16	18	20	24	28
Visit Days	-7	1 [*]	15	29	43	57	71	85	99	113	127	141	169	197
Allowed visit window(days)	-3		±4	±4	±4	±4	±4	±4	±4	±4	±4	±7	±7	±7
Informed consent	X													
Randomization		X												
Apply test medication or comparative intervention		X	X	X	X	X	X	X	X	X [@]	X [@]	X [@]	X [@]	X [@]
Standard ulcer care	X	X	X	X	X	X	X	X	X	X	X	X	X	X
Demographics	X													
Inclusion/Exclusion criteria	X	X												
Disease status	X	X												
Pregnancy test	X													
Physical examination	X	X	X	X	X	X	X	X	X	X	X	X	X	X
Ulcer assessment	X	X	X	X	X	X	X	X	X	X	X	X	X	X
Photography	X	X	X	X	X	X	X	X	X	X	X	X	X	X
12 Lead ECG	X									X				X
X-Rays	X													
Vital signs	X	X	X	X	X	X	X	X	X	X	X	X	X	X
Laboratory tests	X			X		X		X		X				X
Medical history,	X	X												
Concomitant medication	X	X	X	X	X	X	X	X	X	X	X	X	X	X
Assessment of adverse events		X	X	X	X	X	X	X	X	X	X	X	X	X

* : Day 1 should normally be the day of first treatment intake. The day before should normally be Day -1 and there is no Day 0.

This approach is in accordance with CDISC.

: Subject may proceed to Visit 2 as soon as Visit 1 procedures are completed, that means the day of Visit 1 could be same as Visit 2.

& : Visit 10 indicates as the end of study treatment or prematurely discontinuation of study treatment.

@: During the follow-up period, Aquacel[®] Hydrofiber[®] dressing will be applied for subjects who have unhealed or with recurrence wound.

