2.3 Variables

2.3.1 Primary Variable

The primary variable is the number of target ulcers healed in each group within 16 weeks. The primary efficacy outcome is the comparison of the incidence of complete healing of the target ulcer between the two treatment groups at the end of treatment.

For the purpose of this study a complete healing will be defined as complete epithelialization which is maintained with no drainage for at least 2 weeks and is confirmed by a blinded independent evaluator.

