5.1.3 Comparative Period

(Visit 3-Visit 10: Day 15 to Day 113)

The following procedures will be performed in this period:

- Apply test medication or comparative intervention

If complete wound healing by the judgment of independent reviewer happens before Visit 10, the applied test medication (ON101 cream) or comparative intervention (Aquacel® Hydrofiber® dressing) will be stopped at next scheduled visit which will be deemed as V10.

If the wound is unhealed at Visit 10, only Aquacel® Hydrofiber® dressing will be applied.

- Perform physical examinations and obtain vital signs
- Perform laboratory tests including hematology and biochemistry at Visit 4, Visit 6, Visit 8, Visit 10 and at the visit of early permanent discontinuation of study treatment
- 12 Lead ECG examination will be performed at Visit 10 or at the visit of prematurely discontinuation of study treatment
- Perform assessment of foot ulcer status and photography
- Standard ulcer care
- Perform assessment of adverse events
- Record concomitant medication

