5.1.4 Follow-up Period

(Visit 11-Visit 14: Day 127 to Day 197)

The following procedures will be performed in this period:

- Apply Aquacel® Hydrofiber® dressing to the subjects whose wounds are unhealed or recurrent
- Perform physical examinations and obtain vital signs

- Laboratory tests including hematology and biochemistry will be performed at Visit 14 (Week 28) or Visit of early permanent discontinuation during the follow-up period
- 12 Lead ECG examination will be performed at visit 14 (Week 28) or visit of early permanent discontinuation during the follow-up period
- Perform assessment of foot ulcer status and photography
- Standard ulcer care
- Perform assessment of adverse events
- Record concomitant medication

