7.2.1 Full Analysis Set (FAS)

The intent-to-treat (ITT) principal will be applied on the “full analysis set (FAS)”. The FAS includes all subjects who are randomized, irrespective of actual receipt of study intervention. This set will be the primary analyses population for all efficacy data. Under the ITT principle, all participants once randomized are analyzed according to the condition to which they were originally assigned, regardless of adherence with the protocol or the occurrence of adverse events. Thus, using the ITT principle, participants who were randomly assigned to the ON101 cream group but who received partial or none of the ON101 cream, would still be followed and analyzed

as if the participant received the ON101 cream. Participants randomly assigned to the Aquacel® Hydrofiber® dressing group but who received the ON101 cream would be retained in the Aquacel® Hydrofiber® dressing group and analyzed as if they received only the Aquacel® Hydrofiber® dressing.

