7.7 Handling of Missing Data

All available data will be displayed and utilized in data analysis. Under the ITT principle, the subject will be considered as “non-healing” if no available data for post-baseline wound/ulcer healing assessment. Otherwise, the method of last observation carry forward (LOCF) will be used to account for incomplete observation.

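### The plan does not clearly require ulcer assessment to Week 16 for a subject who stops study treatment but stays in the study

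*Combined protocol and SAP*

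**What the plan says.** **Horizon.** Section 2.3.1 states: "The primary variable is the number of target ulcers healed in each group within 16 weeks". Its next sentence places the comparison at the end of treatment instead. Section 7.1 sizes the trial on healing over 16 weeks.

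**What a treatment stop triggers.** Section 3.4 defines a discontinuation as a randomized subject "for whom study treatment is terminated prematurely for any reason", and it separates leaving the intervention from leaving the study. Staying in the study after stopping treatment is therefore foreseen. The footnote to the Schedule of Assessments reads: "Visit 10 indicates as the end of study treatment or prematurely discontinuation of study treatment". Section 3.4 adds: "If a subject withdraws from the study or the study intervention is discontinued prematurely, all procedures as scheduled at the end of the trial" are to be recorded. It does not mention keeping the two-weekly visits. The interim counting rule in section 7.6.2 (also section 10.1 and the Synopsis) treats early withdrawal from the intervention like completing the comparison period.

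**What follows Visit 10.** Section 5.1.4 is headed "Visit 11-Visit 14: Day 127 to Day 197" and includes ulcer assessment and photography. Section 2.2.1 has all subjects followed for 12 weeks after the comparison period.

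**Text pointing the other way.** Section 5.4 continues wound assessment every two weeks until confirmed closure or exit from the study for lack of efficacy. Other treatment stops are not named as an end point of assessment. Section 7.2.1 says subjects who received partial or no ON101 "would still be followed and analyzed" in their assigned group.

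**Missing data.** Under section 7.7 a subject with no post-baseline healing assessment counts as non-healing; otherwise "the method of last observation carry forward (LOCF) will be used to account for incomplete observation".

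**The concern.** A site that follows the footnote, section 3.4 and the printed visit days would do an end-of-treatment visit at the stop and next see the subject at Day 127. The Week-16 status of a subject unhealed at the stop would then be carried forward, although the subject was still in the study and could have been photographed. A closure seen at Day 127 cannot be dated to before Day 113.

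This matters because treatment is open to the investigator (section 4.4), who may also end a subject's involvement (section 3.4). Stopping may therefore differ between arms. The blinded photograph reading protects the assessment of each image. It does not protect the decision that determines which images exist. A different imputation rule would not recover an outcome that was never observed.

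**Working it through.** **1. The plan's own figures.** For 50% versus 30%, two-sided 5% and 80% power, the usual two-proportion formula gives 93 per arm (186) without continuity correction and 103 per arm (206) with it. The plan's 212 exceeds both. Power at 106 per arm is 84.9% at alpha 0.05 and 82.5% at the final alpha of 0.039611, so the claim of at least 80% holds. Inflation: 212 / 0.90 = 235.6, rounded up to 236. Section 3.1 defines evaluable as having taken at least one dose, so the 10% allowance is not an early-stopping rate. Nothing below changes 212, 236 or the alpha boundaries.

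**2. Visit arithmetic.** Visit 10 is Day 113 ±4, that is Days 109–117. Visits 11–14 are Days 127, 141, 169 and 197, which are 14, 28, 56 and 84 days (2, 4, 8 and 12 weeks) after Visit 10. The documents do not say whether they keep those days after an early Visit 10 or are counted from it.

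| Stop at week | Fixed days: next listed assessment | Counted from early Visit 10: weeks | Week 16 listed if counted? |
|---|---|---|---|
| 2 | Week 18 | 4, 6, 10, 14 | no |
| 4 | Week 18 | 6, 8, 12, 16 | yes |
| 6 | Week 18 | 8, 10, 14, 18 | no |
| 8 | Week 18 | 10, 12, 16, 20 | yes |
| 10 | Week 18 | 12, 14, 18, 22 | no |
| 12 | Week 18 | 14, 16, 20, 24 | yes |
| 14 | Week 18 | 16, 18, 22, 26 | yes |

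Example, stop at Day 29: with fixed days the gap is 127 − 29 = 98 days. Counted from the stop, follow-up falls on Days 43, 57, 85 and 113.

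Visit windows do not close the gaps. With fixed days, Visit 11 can be no earlier than 127 − 4 = Day 123. On the counted reading, with a ±7 window, a Week-14 visit reaches 99 + 7 = Day 106 and a Week-18 visit starts at 127 − 7 = Day 120. All lie outside Days 109–117.

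**3. Consequence under each reading.**
- Sixteen-week horizon, fixed days: Week 16 is unobserved after any stop at Weeks 2–14, and an unhealed status is carried forward.
- Sixteen-week horizon, counted from the stop: no Week-16 assessment after stops at Weeks 2, 6 or 10. The plan also does not say whether follow-up photographs count for the primary endpoint.
- End-of-treatment horizon: nothing is imputed, but the time at risk of healing is set by a stop decision made with knowledge of the assignment.

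**4. Illustration (assumed; the documents give no stopping rate).** Let a fraction w of each arm stop unhealed, and let r be the fraction of these who would heal by Week 16. The recorded rate is p − w·r. Take p = 50% and 30%, with r equal to p.

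| w | About how many of 236 | ON101 | Control | Difference | Power |
|---|---|---|---|---|---|
| 0 | 0 | 50% | 30% | 20 points | 86.5% |
| 5% | 12 | 47.5% | 28.5% | 19 points | 83.3% |
| 10% | 24 | 45% | 27% | 18 points | 79.9% |
| 20% | 47 | 40% | 24% | 16 points | 72.1% |

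Power is for a single unadjusted comparison at n = 118 per arm and two-sided alpha 0.039611 (z ≈ 2.058): Φ{[|p₁ − p₂|√n − z√(2p̄(1 − p̄))] / √(p₁(1 − p₁) + p₂(1 − p₂))}. For w = 10%: (0.18 × 10.863 − 2.058 × 0.6788) / 0.6668 = 0.837, giving 79.9%.

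**5. Direction.** At w = 10%:
- r = 25% in both arms: 47.5% versus 27.5%, still 20 points.
- r = 50% in the ON101 arm only: 45% versus 30%, 15 points.
- r = 50% in the control arm only: 50% versus 25%, 25 points.

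With unequal stopping of 15% in control and 5% in ON101, and r = 20%, the shift is 0.15 × 0.20 − 0.05 × 0.20 = 2 points towards ON101. Exchanging the arms reverses the sign.

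**The case against.** A reader might infer that the footnote ends outcome assessment. It does not say so: it labels a visit, and section 5.4, the efficacy-assessment section, continues two-weekly assessment after treatment stops for reasons other than lack of efficacy. This stands, and it is why the point is an unresolved conflict between sections and not an established loss of data.

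A reader might also take the 98-day gap as a fact. It needs the fixed-day reading. Section 2.2.1 starts the 12 weeks after treatment ends, and section 5.1.3 shows that an early visit can be the reference: after healing, treatment "will be stopped at next scheduled visit which will be deemed as V10". Counted from a stop at Day 29, Week 16 is photographed. This also stands, but the counted reading still misses Week 16 after stops at Weeks 2, 6 and 10.

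Section 7.2.1 sets no visit frequency, so photographs at Visits 11–14 do not contradict it outright. Subjects with confirmed healing and an early Visit 10 are unaffected. Several discontinuation reasons (loss to follow-up, sponsor termination, and worsening to Wagner grade 3, which section 5.2.1 describes as exit from the study) leave little or nothing to recover, so the number of subjects concerned may be small.

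Finally, equal stopping with proportional later healing pulls the difference towards zero, which is conservative for a superiority claim. That is true of that scenario only.

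**Conclusion.** The point holds as a conflict that the plan should resolve. The footnote, section 3.4 and the interim counting rule treat a treatment stop as the end of the comparison period. Sections 5.4 and 7.2.1 imply continued assessment, and section 2.3.1 gives two horizons. On no reading is a Week-16 observation secured for every subject who stops treatment and stays in the study, unless section 5.4 is taken to override the rest.

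The documents do not support a claim that the primary comparison is biased by a given amount or in favour of ON101. They give no stopping rate and no healing rate after stopping. The 45% versus 27% figure, and the fall in power from 86.5% to 79.9%, rest on assumed 10% stopping in each arm, all stoppers unhealed at the stop, and later healing at the planned rates. The matter is still more than missing detail: followed literally with fixed follow-up days, the plan replaces obtainable outcomes with carried-forward ones in a trial where the investigator knows the treatment.

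**What to change.** Reconcile sections 2.3.1, 3.4, 5 (footnote), 5.1.4, 5.4, 7.2.1, 7.6.2 and 7.7, with matching wording in the Synopsis, section 10.1 and the SAP:

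- Subjects who stop study treatment but remain in the study keep the listed two-weekly ulcer assessments and photographs through the Week-16 visit including its window (Day 113 ±4). State how Visits 11–14 are timed after that.
- State one horizon for the primary endpoint, and score it from every evaluator-read photograph in that period, whatever the visit label.
- State whether a closure first seen at Week 16 may be confirmed at the next visit, and how a closure not yet confirmed is handled.
- Limit the missing-data rule to assessments actually missed or to subjects who leave the study.
- Say when a subject who has stopped treatment but is still being assessed counts towards an interim analysis.

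**Cost.** Text changes, and a few already listed visits kept for what is likely a small number of subjects. No new procedure is needed, and the sample size and alpha boundaries are unchanged. Photographs already missed cannot be recovered. Because the first interim analysis has been done (124 subjects, section 7.6.2), the change must be documented before the second, by people without access to unblinded results.
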